4.1 Data Handling

Unless otherwise noted, if an observation is missing at a specific scheduled visit/time point, the value at that visit will not be imputed and will be set to missing.

Baseline will be defined as the last measurement taken prior to the start of the IGSC 20% infusion at the Baseline/SC#1 visit.

4.1.1 PK Data Handling

4.1.1.1 Time Window for Pharmacokinetic Analysis

For adult subjects in the PK subset, the time window allowed for serial PK blood sample draws starting at SC#17 (Week 17) and ending at SC#18 (Week 18) in IGSC 20% Treatment Stage 2 is specified in the study protocol. However, if samples are drawn outside the protocol specified (nominal) time or the allowable window, the samples will still be included in the PK analysis as long as the actual sample collection date and clock time for each sample is recorded and the actual elapsed time from the start of infusion can be calculated.

The scheduled time points specified in the protocol will be used in the tables for presenting the summary data of IgG concentrations. The nominal time (hours) will be used in figures for presenting the mean or median concentration vs. time curve. Due to the variable infusion duration in individual subjects, the nominal time may be adjusted by using the average infusion duration among all subjects in the PK population when plotting the mean or median concentration vs. time curve.

The actual elapsed time between the start of the infusion and each PK blood sample draw will be calculated. The PK parameter calculation for each subject will be based on the actual elapsed time instead of the scheduled time or nominal time.

An example of actual elapsed time calculated from the time of the start of the IGSC 20% SC#17 infusion is shown below.

Scheduled Time	Nominal Time (Hours)	Example Actual Elapsed Time (Hours)
Pre-infusion	0	0
Start of infusion	0	0
Immediately at the completion of the infusion	2	2.15
1 day post-infusion	26	26.50
3 days post-infusion	74	73.86
5 days post-infusion	122	123.20
7 days post-infusion (prior to the IGSC 20% SC#18 infusion)	170	169.75

In addition, the actual duration of the infusion will be calculated.

4.1.1.2 IgG Concentration Missing Values

For PK and IgG concentration analysis, any invalid IgG concentration values will be treated as missing, eg, if the sample was hemolyzed or if a planned trough sample was drawn post-

infusion. If necessary, invalid or missing values will be interpolated or extrapolated using PK principles, as appropriate, and such interpolations or extrapolations will be documented in the CSR.

4.1.1.3 Samples Below the Limit of Quantification (BLQ)

Samples with concentration values below the limit of quantification (BLQ) will be imputed as follows:

- BLQ values will be treated as missing.

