3.1.3 Other Variables

Additional PK parameters include average trough concentration of IgG subclasses (IgG1, IgG2, IgG3, and IgG4), and concentration of antibody levels to *S. pneumoniae*, *H. influenzae*, and *C. tetani* (tetanus). Trough measles antibody titers (functional assay) are an exploratory variable for informational purposes.

For the adult (n~20) PK subset, serial samples will be collected immediately before and after SC#17 infusion at steady state. The PK profile will include total IgG concentrations at timepoints over a 7-day period. PK parameters including $AUC_{0-7days}$, C_{max} , and t_{max} will be determined by a noncompartmental model using WinNonlin.

Another efficacy variable is validated infections documented by positive radiograph, fever ($> 38^{\circ}C$ oral or $> 39^{\circ}C$ rectal), culture, or diagnostic testing for microorganisms eg, bacterial,

viral, fungal, or protozoal pathogens (for instance, rapid streptococcal antigen test) will be analyzed separately.

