10 PK ANALYSIS

The Efficacy Evaluable population will be used for the analyses of trough total IgG concentrations, trough IgG subclasses, and trough antibody titers. The analyses of the mean trough total IgG concentrations will be based on the IgG population. The analyses of serial total IgG concentrations and PK parameters will be based on the PK population.

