10.1 Analysis of IgG concentration and dosing data

10.1.1 Analysis of trough total IgG, IgG subclasses, and antibody titers data

Trough concentrations of total IgG during the Screening/Previous Regimen Phase, the IGSC 20% Treatment Stage 1, and the IGSC 20% Treatment Stage 2 will be summarized.

Summaries will be provided for trough concentrations of IgG subclasses (Screening, Baseline/SC#1, SC#13, 24, 36, and Final/Early Termination Visit). Summaries of trough level concentrations of antibody titers against *H. influenzae*, *S. pneumoniae*, and *C. tetani* (tetanus) will also be provided (collected at these same time points).

Trough measles antibody titers (functional assay at Baseline/SC#1, SC#20, and SC#52) will be summarized as an exploratory variable for informational purposes.

All summaries will be provided by study phase and visit for the Efficacy Evaluable population. The summaries will also be provided by adult vs. pediatric subjects and overall.

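### Treating results below the limit of quantification as missing biases the by-visit summaries of IgG subclasses and antibody titers upward wherever such results occur

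*SAP*

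**What the plan says.** SAP 4.1.1.3 is introduced by "Samples with concentration values below the limit of quantification (BLQ) will be imputed as follows", and its only rule is "BLQ values will be treated as missing". So the lead-in announces an imputation and the rule then makes none. The lead-in covers any sample with a concentration value; it names neither total IgG nor the serial samples.

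Three other places bring IgG subclasses and antibodies within reach of that rule:

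- SAP 3.1.3: "Additional PK parameters include average trough concentration of IgG subclasses", with the pneumococcal, H. influenzae and tetanus antibody levels in the same sentence.
- SAP 10 (PK Analysis) assigns the Efficacy Evaluable population to the "analyses of trough total IgG concentrations, trough IgG subclasses, and trough antibody titers".
- SAP 10.1.1: "Summaries will be provided for trough concentrations of IgG subclasses (Screening, Baseline/SC#1, SC#13, 24, 36, and Final/Early Termination Visit"). Titers against the three pathogens are summarised at the same time points, and measles titers at Baseline, SC#20 and SC#52.

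SAP 4 sets the default statistics for these tables: number of non-missing values, mean, SD, median, minimum and maximum. Under SAP 4.1, when an observation is missing at a scheduled visit, "the value at that visit will not be imputed and will be set to missing". SAP 4.1.1.2, on PK and IgG concentration analysis, adds: "If necessary, invalid or missing values will be interpolated or extrapolated using PK principles, as appropriate". It does not say whether a BLQ result that 4.1.1.3 has made missing may be filled in this way.

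**The concern.** A BLQ result is a valid measurement that places the subject below a known limit. Setting it to missing treats that subject like one whose tube was lost. The values that drop out are by definition the lowest at that visit, and n then depends on the level being measured. No tabulated minimum can fall below the assay limit, and no count of BLQ results is planned that would show this.

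Evaluating subclass and antibody levels is a stated objective under Other Objectives in both documents. Eligibility sets a floor for total IgG only (at least 500 mg/dL, Protocol 3.2.1), so nothing in the entry criteria rules out BLQ results for a single subclass or antibody. If some occur, the tables describe only subjects with quantifiable levels while appearing to describe everyone sampled.

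The silence in 4.1.1.2 adds a second risk: a result known to be low could be replaced by a value interpolated from higher neighbouring visits.

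**Working it through.** **No figure to reproduce.** The documents state no LLOQ, BLQ share, mean or SD for any subclass or antibody. The direction follows from the rule; the size needs assumptions.

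**Direction.** For any set of values, removing those below a cut-off can only raise (or leave unchanged) the mean, median and minimum of the rest. This needs no distributional assumption.

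**Size.** Assume log-normal values with log-scale SD s. Let p be the BLQ share and k = z(p) the standard normal quantile that marks the LLOQ.

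- Mean after dropping BLQ, relative to the true mean: Φ(s − k) / (1 − p).
- Median after dropping BLQ, relative to the true median: exp(s · z(p + (1 − p)/2)).
- Mean with LLOQ/2 substituted, relative to the true mean: Φ(s − k) + (p/2) · exp(s·k − s²/2).

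Example at p = 0.10, where k = −1.2816:

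- Mean, s = 0.6: Φ(1.8816)/0.90 = 0.9701/0.90 = 1.078.
- Mean, s = 1.0: Φ(2.2816)/0.90 = 0.9887/0.90 = 1.099.
- Median: z(0.55) = 0.1257, giving exp(0.6 × 0.1257) = 1.078 and exp(1.0 × 0.1257) = 1.134.

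Results for s = 0.6 to 1.0:

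| BLQ share | Mean, BLQ dropped | Median, BLQ dropped | Mean, LLOQ/2 used |
|---|---|---|---|
| 0% | 0 | 0 | 0 |
| 5% | +4.0% to +4.8% | +3.8% to +6.5% | −0.5% to −0.1% |
| 10% | +7.8% to +9.9% | +7.8% to +13.4% | −1.1% to −0.3% |
| 30% | +24.2% to +33.8% | +26.0% to +47.0% | −3.9% to −1.0% |

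With LLOQ/2 the median is unchanged as long as fewer than half the results are BLQ.

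**Sensitivity to a narrower spread.** At s = 0.4 the mean after dropping BLQ rises by 3.1%, 6.0% and 17.5% at the same three non-zero shares. The substitution then does somewhat worse: at 30% BLQ, Φ(0.9244) + 0.15 · exp(−0.2098 − 0.08) = 0.8224 + 0.1123 = 0.935, or −6.5%.

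**Comparisons between visits.** Baseline and follow-up were simulated as correlated log-normals (log-SD 0.8, 10⁶ draws, the same LLOQ at both visits), with BLQ results dropped. The first three rows use a true follow-up to Baseline ratio of 1.5 and 10% BLQ at Baseline.

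| Setting | True change | Change after dropping BLQ |
|---|---|---|
| Difference of visit means | 0.69 | 0.63 (smaller) |
| Paired arithmetic change, correlation 0.5 / 0.8 | 0.69 | 0.72 / 0.74 (larger) |
| Paired log change, correlation 0.5 / 0.8 | 0.41 | 0.36 / 0.38 (smaller) |
| 10% of subjects BLQ and unchanged at both visits, the rest rising by 20% | 0.390 | 0.433 (larger) |
| Same distribution at both visits | 0 | 0 (no bias) |

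The direction depends on the scale, on pairing and on where the BLQ results fall.

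**The case against.** The strongest reply is that this may never matter. Every subject has been on stable replacement for at least 3 months with total IgG of at least 500 mg/dL, and the documents show no sign that BLQ results are expected. The 30% row is an illustration without support in the text; at 1% BLQ the mean moves by at most about 1%. This stands, and it limits the size. It does not justify the rule, because the correction has no effect if no BLQ result occurs.

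Scope can also be disputed. The rule follows sections on serial PK sampling times and missing IgG concentrations, and the SAP never says that it covers pathogen titers or the measles functional assay. That is fair, but the lead-in is general, SAP 3.1.3 and 10 treat these analytes as PK data, and no other BLQ rule exists for them.

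The loss is not fully hidden either: n is tabulated, and SAP 4 calls for listings of all collected data. A reader who sees n fall still cannot tell BLQ results from lost samples, and the tabulated statistics stay biased.

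A reader might go further and infer that the rule shrinks the change from Baseline. The documents do not support this. The SAP plans change from Baseline for laboratory tests (11.2) and vital signs (11.3), not for subclasses or titers, and the simulation shows no fixed direction. Bias in geometric means would be larger, but SAP 10.1.3 and 10.3 plan those only for serial total IgG and PK parameters.

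Nor are these summaries a test of whether antibody levels are maintained. The objective of comparability with the previous regimen concerns total IgG alone; subclass and antibody levels are simply to be evaluated, and measles titers are exploratory.

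**Conclusion.** The point holds for the by-visit summaries. Following SAP 4.1.1.3 as worded biases the mean, median and minimum of IgG subclasses and antibody titers upward whenever BLQ results occur. The size rests entirely on the assumed log-normal spread and BLQ share, and could be nil.

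The consequence is limited. No hypothesis test or success criterion uses these variables. The primary Poisson analysis of serious bacterial infections does not draw on them, and BLQ total IgG is not expected in subjects who enter at 500 mg/dL or more, so the trough comparison with the previous regimen is not affected. This is an inexpensive improvement to descriptive tables and no threat to the trial's conclusions.

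**What to change.** Amend SAP 4.1.1.3 before database lock. For IgG subclasses and all antibody titers, including measles:

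- set BLQ results to LLOQ/2 in summaries and keep the subject in n;
- report the number and percentage of BLQ results per analyte and visit;
- state that the interpolation and extrapolation in 4.1.1.2 do not apply to BLQ results.

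The rule that treats BLQ as missing may stay for serial total IgG. The new text should also resolve the mismatch between the lead-in, which speaks of imputing, and the rule.

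The cost is a line or two of text and a count in each table. Reported means may be slightly lower than under the present rule. LLOQ/2 is a convention with a small bias of its own: about −4% to 0% in the arithmetic mean for a log-SD of 0.6 to 1.0 and up to 30% BLQ. The BLQ counts let a reader judge whether that matters.

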4.2 Analysis Populations

Safety population

The Safety population will include all subjects who have received any amount of IGSC 20% and will be used for safety analysis.

Efficacy Evaluable population

The Efficacy Evaluable population will include all subjects who have received at least one dose of IGSC 20% and will be used for efficacy analysis.

IgG population

The IgG population will consist of all subjects who receive any amount of IGSC 20% and have total IgG concentration data to facilitate the comparison of mean trough IgG concentration during the IGSC 20% phase versus the pre-treatment phase.

PK population

The PK population will consist of all adult subjects in the PK subset who have received IGSC 20% and have sufficient serial IgG concentration vs. time data to facilitate calculation of AUC PK parameters. The PK population will be used for the analyses of the PK parameters.

Adequate treatment compliance will be considered when determining valid concentration-time data for inclusion in the PK analyses. The values or profiles deemed not reliable due to treatment non-compliance or other reasons (eg, blood sampling/collection or testing issues) will be excluded from the PK analyses and flagged in the listing. Any subject who has at least one major protocol deviation which might have an impact on the PK analyses (to be defined in a data review meeting prior to database lock) will be excluded from the PK population. PK parameters (ie, AUC values) will only be calculated for PK profiles with at least 4 quantifiable samples following data imputations (if applicable).

4.3 Sample Size Considerations

Assuming that the true rate of the SBIs is 0.25 per subject per year, 40 subjects treated for one year for IGSC 20% will provide at least 90% power to reject the null hypothesis of a SBI rate greater than or equal to 1.0 per person per year, using a one-sided test at the 0.01 level.

In order to obtain a total of 40 PI subjects including 20 adult and 20 pediatric evaluable subjects, approximately 60 subjects will be enrolled and treated in the study. This sample size is to allow for a moderate to high early discontinuation rate seen in other similar studies.

4.4 Interim Analysis

No interim analysis is planned to be performed.

5 SUBJECT DISPOSITION

Subject disposition will include the number of subjects screened, number of subjects treated, number and percentage of subjects in each analysis population, and number and percentage of subjects completing the study by study phase and overall. Subject disposition will also be summarized by adult vs. pediatric subjects and overall.

The number and percentage of subjects discontinuing early from the study will be summarized for primary reasons of discontinuation by study phase and overall. Also, the number and percentage of screening failures will be summarized for primary reasons of ineligibility.

Disposition status will be listed for all subjects.

6 PROTOCOL DEVIATIONS

Protocol deviations will be identified during the study and evaluated before the database lock. The type/category of protocol deviations and severity (ie, minor or major) will be summarized and listed.

7 DEMOGRAPHY AND MEDICAL HISTORY

7.1 Demographic and Baseline Characteristics

Demographic and baseline characteristics including sex, race, ethnicity, age, age categories (≤ 16 [with sub-categories: $\geq 2 - \leq 5$, $> 5 - \leq 12$, $> 12 - \leq 16$], > 16 [with sub-categories: $> 16 - < 65$, ≥ 65] years), height, weight, screening total IgG level, subject entry status, and frequency of the IgG dose at entry will be summarized for the Efficacy Evaluable population. The primary immunodeficiency and IgG treatment history will also be summarized. The summaries will be provided by adult vs. pediatric subjects and overall.

All demographic and baseline characteristics data will be listed.

7.2 Medical History

Medical history will be coded using the Medical Dictionary for Regulatory Activities (MedDRA) and summarized/listed. The summaries will be provided by adult vs. pediatric subjects and overall.

8 CONCOMITANT MEDICATION AND TREATMENT

8.1 Prior and Concomitant Medication

All medications as documented by the investigator will be coded using Anatomical Therapeutic Chemical (ATC) classification codes via the World Health Organization Drug Classification Dictionary (WHO-DD). All medications will be summarized and sorted alphabetically by medication class (ie, ATC level 2) and medication sub-class (ie, ATC level 4). If the ATC level 2 or 4 term is missing, the higher ATC level term will be used in the medication summary table and data listing.

Prior medications and concomitant medications will be summarized separately either overall (prior medications) or by study phase (concomitant medications). Prior medications are defined as any medication ended prior to the start of study treatment (ie, start of the infusion at Baseline/SC#1). Concomitant medications are defined as any medication started on or after the start of study treatment or any medication taken prior to the start of study treatment and continued after the start of study treatment during the study.

The following conservative imputation rules will be used for missing or partial end date/time information in order to determine whether a medication is prior or concomitant (ie, the unknown portions of a medication end date/time will be assumed to be as late as possible):

- Note: year is required on the eCRF, except for ongoing medication
- If the entire end year, date and time values are missing (ie, ongoing medication), then no imputation is performed and the medication will be assigned to the “concomitant” category
- If the month is missing, impute “December”
- If the day is missing, impute the last day of the month (ie, “28/29/30/31” depending on the year and month)
- If the hours are missing, impute “23”
- If the minutes are missing, impute “59”

The imputed medication end date/time will then be compared with the start of study treatment to determine if the medication is prior or concomitant.

Note the imputed end date/time will only be used to determine whether a medication is prior or concomitant. The start/end dates/times reported on the eCRFs will be presented in the listings.

8.2 Extent of Study Treatment Exposure and Compliance

8.2.1 Extent of Study Treatment Exposure

Duration of exposure will be determined for each IGSC 20% study phase and overall.

Duration of exposure in days

For the IGSC 20% Treatment Stage 1, the duration of exposure in days will be calculated as:

$$\text{Infusion date of SC\#14} - \text{Infusion date of Baseline/SC\#1}$$

For the IGSC 20% Treatment Stage 2, the duration of exposure will include not only the total time between the first and last SC infusion during the treatment stage, but also include an additional 7 days to take into account total exposure time to the study drug since each SC infusion is administrated weekly. The duration of exposure in days will be calculated as:

$$(\text{Infusion date of SC\#52} - \text{Infusion date of SC\#14}) + 7$$

Similarly, for the overall IGSC 20% treatment phase, the duration of exposure in days will be calculated as:

$$(\text{Infusion date of SC\#52} - \text{Infusion date of Baseline/SC\#1}) + 7$$

For subjects who prematurely discontinued from the study, the duration of exposure in days for the study phase in which the discontinuation occurred and for the overall treatment phase will be similarly calculated as:

$$(\text{Last SC infusion date in the study phase} - \text{First SC Infusion date in the study phase}) + 7$$

Duration of exposure expressed in other units

Duration of exposure in weeks will be calculated as:

$$\text{Duration of exposure in days} / 7$$

Duration of exposure in years will be calculated as:

$$\text{Duration of exposure in days} / 365.25$$

Duration of infusion

Duration of infusion in minutes will be calculated for each infusion as:

$$\text{Stop time of infusion} - \text{Start time of infusion}$$

Dose Conversion Factor

In this study, the study drug dose (ie, expected dose as prescribed) in mg/kg/week will be collected on the eCRF at all SC visits.

At each SC visit, the actual dose conversion factor from the previous regimen to IGSC 20% dose will be calculated as follows:

For subjects on previous IV regimen:

$$\text{Dose (mg/kg)} / [\text{pIV dose (mg/kg)} / 3 \text{ or } 4 \text{ (pIV dosing interval in weeks between infusions)}]$$

For subjects on previous SC regimen:

$$\text{Dose (mg/kg)} / [\text{pSC dose (mg/kg)} / \text{pSC dosing interval in weeks between infusions}]$$

In addition, the actual average dose conversion factor from the previous regimen to IGSC 20% dose will be calculated for each study phase and the overall IGSC 20% treatment phase.

First, the average weekly dose (mg/kg) will be calculated as:

$$\text{Total dose (mg/kg)} / \text{Total number of infusions}$$

The actual average dose conversion factor will then be calculated as follows:

For subjects on previous IV regimen:

$$\text{Average weekly dose (mg/kg)} / [\text{pIV dose (mg/kg)} / 3 \text{ or } 4 \text{ (pIV dosing interval in weeks between infusions)}]$$

For subjects on previous SC regimen:

$$\text{Average weekly dose (mg/kg)} / [\text{pSC dose (mg/kg)} / \text{pSC dosing interval in weeks between infusions}]$$

For each study phase, the duration of exposure (weeks), the number of infusions received, the total volume infused (mL), and the duration of infusion (minutes) will be summarized.

Further, infusion interruptions will be summarized. The distribution and number of SC infusion sites will be separately summarized. The number and percentage of subjects with actual dose conversion factor different from 1 and the actual dose conversion factor will be summarized for each SC visit, each study phase, and the overall IGSC 20% treatment phase. The summaries will also be provided by adult vs. pediatric subjects and overall.

8.2.2 Compliance

Infusion compliance, treatment compliance, and overall compliance will be calculated separately for each IGSC 20% study phase.

Infusion Compliance

Infusion compliance (%) will be calculated as:

$$(\text{Number of SC infusions received} / \text{Number of SC infusions expected}) \times 100\%$$

For subjects who completed the study, the number of SC infusions expected will be 13 for IGSC 20% Treatment Stage 1 and 39 for IGSC 20% Treatment Stage 2. For subjects who prematurely discontinued from the study during IGSC 20% Treatment Stage 1, the number of SC infusions expected will be the SC week number of the last SC infusion for IGSC 20% Treatment Stage 1 and 0 for IGSC 20% Treatment Stage 2. For subjects who prematurely discontinued from the study during IGSC 20% Treatment Stage 2, the number of SC infusions expected will be 13 for IGSC 20% Treatment Stage 1 and (the SC week number of the last SC infusion – 13) for IGSC 20% Treatment Stage 2.

Treatment Compliance

Treatment compliance (%) will be calculated as:

$$(\text{Total volume infused [mL]} / \text{Total volume expected [mL]}) \times 100\%.$$

The total volume infused will be calculated as the sum of the volume infused at each SC visit collected in the eDiary.

The total volume expected will be derived as follows:

First, at each visit, the volume expected (mL) at that visit will be calculated as:

$$\text{Dose expected (mg/kg)} \times \text{Weight (kg)} / \text{Concentration of 200 (mg/mL)}$$

If at any visits the dose expected and/or weight was not collected, the latest available values among the prior visits will be used.

The total volume expected will then be calculated as the sum of the volumes expected from the first planned visit of the study phase to the last planned visit of the study phase if a subject completed the study phase or to the visit of the last SC infusion if the subject did not complete the study phase.

Overall Compliance

The overall compliance (%) will be calculated as:

$$(\text{Infusion compliance} \times \text{Treatment compliance}) / 100$$

Infusion compliance, treatment compliance, and overall compliance will be listed and summarized by IGSC 20% study phase and overall. The number and percentage of subjects with compliance between 80% and 120% will also be summarized. The summaries will also be provided by adult vs. pediatric subjects and overall.

Additional consideration regarding compliance will be given when determining legitimacy for inclusion of total IgG concentration data for the calculation of the PK parameters. For example, subjects' treatment or infusion compliance (%) during the 4 consecutive weeks

prior to SC#17 PK assessment, ie, from SC#14 to #17, will be evaluated. Reasons for excluding total IgG concentration data or a subject from the analysis of PK parameters will be documented in the CSR.

